12.1	FUNDING SOURCE.....	25
12.2	COSTS TO THE PARTICIPANT	25
12.3	PARTICIPANT REIMBURSEMENTS OR PAYMENTS	25
13	CONFLICT OF INTEREST POLICY.....	25
14	REFERENCES	26
15	ATTACHMENTS	27
15.1	OPIOID EQUIVALENTS.....	27
15.2	BASELINE ASSESSMENTS.....	ERROR! BOOKMARK NOT DEFINED.
15.3	MEDICATION USAGE RECORD	ERROR! BOOKMARK NOT DEFINED.

CONFIDENTIAL

This material is the property of the NYU School of Medicine and Langone Medical Center. Do not disclose or use except as authorized in writing by the study sponsor

List of Abbreviations

ACLR	Anterior Cruciate Ligament Reconstruction
BPTB	Bone Patellar Tendon Bone
IPACK	Interspace between the Popliteal Artery and Capsule of the Knee
ACB	Adductor Canal Block
ASA	American Society of Anesthesiologist Score
BMI	Body Mass Index
DOS	Day of surgery
VAS	Visual analog scale
AE	Adverse event
SAE	Serious adverse event
IV	Intravenous
ITT	Intention-to-treat
PACU	Post-Anesthesia Care Unit
PO	Taken orally
CI	Confidence interval
SD	Standard deviation; a parameter that characterizes a population distribution
SE	Standard error
ANOVA	Analysis of variance; a linear model
NSAID	Non-steroidal anti-inflammatory drug

CONFIDENTIAL

This material is the property of the NYU School of Medicine and Langone Medical Center. Do not disclose or use except as authorized in writing by the study sponsor

Protocol Summary

Title	Adductor Canal Block and IPACK Block vs. Isolated Adductor Canal Block for Post-Operative Analgesia Following ACL Reconstruction with Bone Patellar Tendon Bone Autograft: A Single Center Randomized Placebo-Controlled Trial.
Brief Summary	A randomized, single-blind, single-center study measuring the effects of adductor canal block combined with IPACK infiltration compared to adductor canal block alone on post-operative pain and opioid consumption in patients undergoing ACL reconstruction with Bone Patellar Tendon Bone Autograft
Objectives	To determine if the addition of an IPACK block to the standard adductor canal block is superior to an isolated adductor canal block in controlling post-operative pain and decreasing postoperative opioid consumption in patients undergoing ACLR with Bone Patellar Tendon Bone Autograft
Methodology	Randomized, single-blind, single-center study
Endpoint	Primary Endpoint: Opioid utilization for the first 72 hours after surgery, including during surgery, calculated as morphine equivalent. Secondary Endpoints: Opioid consumption Post-operatively Patient reported VAS scores in PACU Length of stay in PACU Patient reported VAS scores on POD 1, POD 2, POD 3, POD 7 Reaction to IPACK block Incidence of postoperative complications
Study Duration	The study will continue until 50 subjects are enrolled per arm, to allow for potential dropout and increased power.
Participant Duration	Each participant will be enrolled on DOS and complete their final follow up on postoperative day seven.
Duration of IP administration	Once during surgery
Population	50 patients per study arm scheduled for ACLR with BPTB autograft
Study Sites	NYU Langone Orthopedic Hospital and NYU Ambulatory Surgery Center at 38 th street
Number of participants	100
Description of Study Agent/Procedure	Patients in both the study and control group will receive the standard of care adductor canal block composed of 15 mL of Bupivacaine (0.25%). Patients in the study group will receive the additional IPACK block performed using 20 mL of Bupivacaine (0.25%) injected into the interspace between the popliteal artery and capsule of the knee. Patients will be blinded to their group allocation.
Reference Therapy	Reference is isolated adductor canal block
Key Procedures	Adductor canal block 15 mL 0.25% Bupivacaine, IPACK block with 20 mL 0.25% bupivacaine

CONFIDENTIAL

This material is the property of the NYU School of Medicine and Langone Medical Center. Do not disclose or use except as authorized in writing by the study sponsor

Statistical Analysis	Continuous and categorical baseline characteristics will be compared using Hedges standardized difference. Normally distributed data will be compared using t tests while non-normally distributed continuous outcomes will be assessed using the Mann-Whitney U test.
----------------------	--

CONFIDENTIAL

This material is the property of the NYU School of Medicine and Langone Medical Center. Do not disclose or use except as authorized in writing by the study sponsor

1 Background and Specific Aims

Anterior cruciate ligament (ACL) reconstructions are among the most commonly performed outpatient orthopedic procedures, with approximately 400,000 ACLRs performed each year.¹ Outcomes following ACL reconstruction (ACLR) are excellent, with low rates of graft failure and high rates of return to pre-injury function.^{2,3} Despite these positive outcomes, post-operative pain and discomfort is a commonly cited complaint following ACLR. Pain control following ACLR is multimodal, including peripheral nerve blocks intraarticular injections, oral, and IV medications.⁴ However, given the rise in reported rates of addiction to opioids and high prescribing patterns among orthopedic surgeons, alternative pain control modalities must be explored.^{4,5}

For arthroscopic ACLR with Bone Patellar Tendon Bone (BPTB) autograft, assuming there are no contraindications, anesthesiologists at our institution perform a block of the saphenous nerve via the adductor canal, also known as adductor canal block (ACB). When compared to a femoral nerve block (FNB), the adductor canal block has been shown to have equivalent analgesia without the undesired quadriceps weakness associated with FNBs.⁶⁻⁸ While these peripheral blocks have proven to be effective, they spare sensory function to the posterior knee compartment, leading to posterior knee pain postoperatively. This portion of the knee, innervated by the common peroneal nerve, obturator nerve, and tibial nerves, can be a source of pain for patients following knee surgery.⁹ The IPACK block seeks to reduce pain in the posterior aspect of the knee, while sparing quadriceps strength. There have been several studies looking at the use of IPACK block in arthroplasty; these studies have found a short term improved analgesic effect of decreased pain scores while in the post anesthesia care unit (PACU), however they did not find significant differences in amount of narcotics used postoperatively.^{6,9-11} In a study looking at ACLR with femoral block + IPACK and local infiltration anesthesia, patients who underwent IPACK and femoral block had lower postoperative IV morphine consumption within 24 hours of surgery.¹² To date, there have been no studies looking at analgesia using IPACK block combined with adductor canal block for patient undergoing ACLR in the ambulatory setting. With this blinded randomized control trial, we seek to elucidate the added benefit of an IPACK block and to determine if it leads to improved pain control and decreased opioid use following ACLR with BPTB autograft.

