1.3 Objectives and Purpose

The goal of this study is to determine if the addition of IPACK block to the standard of care adductor canal block is superior to an isolated adductor canal block in decreasing postoperative pain, decreasing opioid consumption, and leads to increased duration of analgesia in patients undergoing ACLR. The primary objective will be to compare opioid utilization between the two arms within the first 72 hours after surgery, including intraoperatively, as measured by morphine equivalents. Our secondary objectives are measuring patient reported pain scores in PACU at 24 hours, 48 hours, and 72 hours, and at the first postoperative visit (POD 7).

2 Study Design and Endpoints

Arm 1: Experimental	Arm 2: Control
Sample Size: 50	Sample Size: 50
Medication: 15 mL of 0.25% Bupivacaine block of the saphenous nerve injected under ultrasound guidance via adductor canal and IPACK block with 20 mL of 0.25% Bupivacaine injected into the Interspace between the Popliteal Artery and Capsule of the Knee	Medication: 15 mL of 0.25% Bupivacaine block of the saphenous nerve injected under ultrasound guidance via adductor canal

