2.1 Description of Study Design

RECRUITMENT PHASE/CONSENTING PHASE:

Surgeons will identify eligible patients via Epic during their initial clinic visit and discuss the study. Surgeons will provide research coordinator with the name and medical record number of eligible patients. If the patient meets the inclusion criteria outlined below and is agreeable, subjects will be first introduced to the study during one of their presurgical clinic visits and then consented on the day of surgery by a member of the research team. Patients will be made acquainted with the study prior to surgery. On DOS when they arrive 1.5/2 hours before surgery, we (study team members) will consent them in a private room and provide ample time to discuss and review any questions or concerns they may have.

BASELINE ASSESSMENTS:

Subjects will complete a baseline VAS McGill Pain scale, Kujala, KOOS-PS and Tegner Activity Scale

RANDOMIZATION PHASE:

Subjects scheduled to undergo ACLR with BPTB autograft will be randomized to either ACB with IPACK block or to ACB only. A randomization scheme will be created prior to start of study enrollment using the randomizer.org website to generate the assignment. Block randomization is commonly used in clinical trial design to reduce bias and achieve balance in the allocation of participants to treatment arms throughout the course of the study. Randomized block design allows us to account for variables so that observed differences are largely due to true differences between treatments and not to the variable. We will create blocks of four patients and in each block, two patients will be assigned to the IPACK + ACB group, and two to the ACB only

CONFIDENTIAL

This material is the property of the NYU School of Medicine and Langone Medical Center. Do not disclose or use except as authorized in writing by the study sponsor

group. Thus, patients in both groups will be evenly spread from the beginning to the end of the study.

A research coordinator will place the randomization results in sealed envelopes prior to recruitment. Each subject enrolled in the study will be assigned a number and the sealed envelope assigning the subject to the IPACK + ACB or ACB only will be opened on the day of surgery after the patient has signed consent agreeing to participate in the study.

Patients will be blinded to their group allocation. During peripheral block patients are sedated and postoperatively, the areas of infiltration will be covered by bandage.

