TREATMENT PHASE:

Patients in both the study and control group will receive the standard of care adductor canal block. This consists of 15mL of bupivacaine (0.25%) Injected under ultrasound guidance in the saphenous nerve via the adductor canal. Patients in the study group will receive the additional IPACK block performed using 20 mL of bupivacaine (0.25%) injected into the interspace between the popliteal artery and capsule of the knee.

[figure not shown]
POST-OPERATIVE PHASE:

After initial recruitment, subjects' pain will be assessed via visual analog scale (VAS) by nursing staff during the post-operative period as per standard of care in the post anesthesia care unit, and by the research staff prior to leaving the surgical center. The VAS pain scores are collected and documented in the patient's electronic medical record. Additionally, a standardized regimen of pain medication will be given to all subjects who are enrolled. The pain medications given to patients are standard of care medication 325-5 mg Percocet and vary based on pain level. This is determined by the clinical staff caring for each patient. While the patient is in the PACU prior to discharge, an authorized research member will visit the patient and obtain a pain score using the VAS and McGill Pain Scale. Data on PACU opioid use documented in the electronic medical record will be collected. On POD1, POD 2 and POD 3, a phone call or email survey will be sent to the patient to collect additional data on opioid use at home as well as a VAS score at 24, 48, and 72 hours after surgery.

CONFIDENTIAL

This material is the property of the NYU School of Medicine and Langone Medical Center. Do not disclose or use except as authorized in writing by the study sponsor

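### The title says placebo-controlled but no placebo or sham is described, and the protocol does not require matching dressings in the two arms, so patient blinding is not assured

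*Combined protocol and SAP*

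**What the plan says.** The Protocol Summary gives the title as "A Single Center Randomized Placebo-Controlled Trial". The Brief Summary row of the same table calls it a "randomized, single-blind, single-center study", and the Reference Therapy row reads "Reference is isolated adductor canal block".

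The control entry in the arm table at the head of Section 2 is "Medication: 15 mL of 0.25% Bupivacaine block of the saphenous nerve injected under ultrasound guidance via adductor canal", with nothing further. The Description of Study Agent/Procedure row of the Summary, Section 2.1 (Treatment Phase) and Section 4.1.1 agree. In each, both arms receive the ACB and only the study group receives the IPACK injection. Section 4.1.2 also describes standard care as the ACB.

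On masking, Section 2.1 (Randomization Phase) says "Patients will be blinded to their group allocation" and gives the means in one sentence: "During peripheral block patients are sedated and postoperatively, the areas of infiltration will be covered by bandage". Section 6.4, although its heading includes masking, covers only how the allocation list and envelopes are produced and handed over. Section 6.1 justifies the intention-to-treat analysis partly on the ground that the patient is blinded.

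**The concern.** There are two linked problems.

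First, the title claims a control condition that the arm descriptions do not contain. A reader who takes it at face value would credit the result with protection against expectation effects that only a placebo or sham would give.

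Second, the masking procedure is under-specified where it matters. Sedation hides the injection while it is given, but it does not hide a dressing seen afterwards. The study has been explained to patients before surgery (Sections 2.1 and 3.4), so they know that one arm has an additional block.

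The patient is the only party the protocol says is blinded. VAS in PACU and on POD 1, 2, 3 and 7 is the patient's own report, and opioid use at home is reported by phone or email. If patients could infer their arm, both could shift for reasons unrelated to analgesia.

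**Working it through.** **Step 1. Title against arms.**

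| Place | What controls receive |
|---|---|
| Summary, Title | labelled placebo-controlled, but also names isolated ACB as the comparator |
| Summary, Reference Therapy | isolated ACB |
| Summary, Description of Study Agent/Procedure | ACB |
| Section 2, arm table | ACB |
| Section 2.1, Treatment Phase | ACB |
| Section 4.1.1 | ACB |
| Section 4.1.2 | ACB |

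The word placebo appears only in the title. No saline or sham injection appears anywhere in the available text. The design described is an add-on comparison, ACB plus IPACK against ACB alone, blinded to the patient.

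**Step 2. Dressings by arm.** Apply the Section 2.1 sentence to the arm descriptions. A control has one infiltrated area (adductor canal). An IPACK patient has two (adductor canal, and the space between the popliteal artery and the knee capsule). Covering the infiltrated areas and no others would give different dressings by arm. The sentence neither requires nor rules out a covering at the IPACK site in controls.

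**Step 3. Which outcomes are exposed.**
- VAS at every time point: directly exposed, being patient-reported.
- Home opioid use: directly exposed. It enters the primary endpoint whether the window is 24 hours (Section 6.2) or 72 hours (Summary, Section 1.3).
- PACU opioid use: indirectly exposed. It is taken from the medical record, and Section 2.1 leaves the medication given to clinical staff, but it varies with the pain the patient reports.
- Intraoperative opioid use: not exposed to patient expectation.

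**Step 4. Sensitivity range.** The plan has no figure to reproduce here. Two inputs are assumptions, not taken from the documents: the fraction of patients who infer their arm (25% to 100%) and the shift that this knowledge produces (0.1 to 0.3 SD).

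Bias = fraction aware × shift. The lowest value is 0.25 × 0.1 = 0.025 SD and the highest is 1.00 × 0.3 = 0.30 SD.

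With no true effect, a bias of *d* SD gives the two-sided t test a noncentrality of *d* × √(n/2). With n = 50 per arm, √25 = 5. With 98 degrees of freedom and α = 0.05 the critical value is 1.984.

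| Assumed bias (SD) | Noncentrality | False-positive rate |
|---|---|---|
| 0 | 0 | 5.0% |
| 0.025 | 0.125 | 5.2% |
| 0.1 | 0.5 | 7.9% |
| 0.2 | 1.0 | 16.8% |
| 0.3 | 1.5 | 32% |

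These rates apply to an outcome whose arm difference is shifted by the whole of *d*. The primary endpoint is a sum that includes the unexposed intraoperative part, so a given expectation effect on home use need not carry over to it in full.

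**The case against.** The strongest reply is that the control is stated correctly everywhere except in one phrase of the title. The title itself names isolated ACB as the comparator, and the rows below it say single-blind. On that view the label is a wording slip. This is fair as to how easily an attentive reader is corrected. But the title states a property of the design, and it is what is seen first and most widely, so it still has to agree with the arms.

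On blinding, a reader might infer that the dressings will show patients which arm they are in. The documents do not support that. Section 2.1 offers the bandage as a means of blinding and uses the plural for patients in general. It does not say that only injected sites are covered, that each site has a separate dressing, or that patients could tell what a dressing signifies. Matching coverings in both arms fit the text. Patients are also sedated during the block. What stands is narrower: matching is not specified, and the literal reading gives different dressings.

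A reader might also take one of the higher false-positive rates as the trial's expected error rate. That does not follow either. Both inputs are assumed, and at the low end the inflation is negligible.

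Finally, the study schematic, a figure and the consent pages are not in the available text. A sham described only there would not have been seen, though it would conflict with the isolated ACB reference.

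**Conclusion.** The contradiction between title and arms is definite on the available text. As the arms now stand, this is a patient-blinded trial with no placebo or sham. Omitting a sham is a legitimate design choice and is not itself the criticism.

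The masking gap is real, but its consequence is unproven. The protocol does not require matching dressings, so blinding for VAS and home opioid use is not assured. Actual unblinding is not established.

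The range in the working shows only how sensitive a 50-per-arm comparison is to the assumed inputs. It is not an estimate of bias in this trial. The point merits correction because the masking change is nearly free and protects outcomes that depend on the patient's own report.

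**What to change.** 1. Remove placebo-controlled from the title and describe the trial as patient-blinded with no placebo or sham. If the investigators do intend some control procedure at the IPACK site, the title and all the arm descriptions must be reconciled to say so.
2. State in Section 2.1 that identical dressings are placed at both the adductor canal site and the IPACK site in every patient, regardless of arm. If this is already the practice, one sentence closes the gap.
3. Optionally, ask each patient to guess the allocation and report the answers by arm. This is best done before PACU discharge, because later guesses may reflect how well the block worked rather than failed masking.
4. If a bias figure is reported, present it as a range with its assumptions stated, and note that intraoperative opioid use is not exposed to patient expectation.

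The cost is a wording amendment, one extra bandage per control patient and, if chosen, one question at the existing PACU contact. Sample size, visits and analysis are unchanged.

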1.1 Specific Aims

This study will aim to compare ACB + IPACK block versus ACB only for posterior knee pain in patients undergoing ACLR with BPTB autograft.

AIM 1: To determine if the addition of IPACK block to the standard of care ACB is superior in terms of decreasing opioid consumption, decreasing pain, and increasing analgesia duration following anterior cruciate ligament reconstruction.

1.2 Statistical Hypothesis

We hypothesize that patients who receive an IPACK block plus an ACB will have lower postoperative opioid consumption over the first 24 hours (measured in morphine equivalents) compared to those who an isolated ACB following anterior cruciate ligament reconstruction. Furthermore, the study group will report lower postoperative pain scores on POD1 than the control group. Failing to reject the null would signify that the IPACK block has no clinically relevant difference on post-operative opioid consumption outcomes following ACLR with BPTB autograft.

CONFIDENTIAL

This material is the property of the NYU School of Medicine and Langone Medical Center. Do not disclose or use except as authorized in writing by the study sponsor

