5.2 Potential benefits

Study subjects may experience better pain control, improved satisfaction, decreased need for opioids and reduced incidence of side effects. If the study is not inconclusive, the study's results may benefit future patients by showcasing that addition of IPACK block improves pain control in the first 24 hours of an ACLR.

6 Statistical Analysis

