6.2 Analysis of Endpoints

Primary Endpoints:

1. Opioid utilization for the first 24 hours after surgery, including during surgery, calculated as oral morphine equivalent.

CONFIDENTIAL

This material is the property of the NYU School of Medicine and Langone Medical Center. Do not disclose or use except as authorized in writing by the study sponsor

Secondary Endpoints:

1. Patient reported VAS scores in PACU
2. Length of stay in PACU
3. Patient reported VAS scores on POD 1, POD 2, POD 3, POD7
4. Reaction to IPACK block
5. Mid-term functional outcomes will be assessed at 6 months: VAS, KOOS-PS, KUJALA, Tegner Activity Scale, strength, ROM.

Normally distributed data such as the primary outcome variable will be compared using the two-sample t-test. In the case that the data are not normally distributed, the Wilcoxon rank-sum test will be used instead. Categorical variable will be compared using the Chi-Squares unless other tests such as the Fisher's exact test are more appropriate.

All endpoints will be evaluated as fits the data set with graphical figures such as scatter plots, box-and-whisker plots, and frequency histograms to visualize the distribution of these outcomes and their relationships to covariates and treatment assignment. When appropriate descriptive graphical and tabular methods will also be estimated and presented in a graphical figure.

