6.3 Sample Size

Using a 2-sided, 2-sample t test, an α value of 0.05, a power analysis revealed that 42 subjects were needed per group to detect a moderate effect size with a power of 0.80. We chose to enroll 50 subjects per arm to allow for potential dropout and an increased power.

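### Section 1.2 reads any non-significant result as no clinically relevant difference, yet by the plan's own power 20% of trials with 42 per arm (about 13% with 50) would miss the effect it is sized for

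*Combined protocol and SAP*

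**What the plan says.** Section 1.2 (Statistical Hypothesis) ends with the only rule in the documents for interpreting a null result: "Failing to reject the null would signify that the IPACK block has no clinically relevant difference on post-operative opioid consumption outcomes". Nothing in section 1.2 or section 6 qualifies it.

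The surrounding plan reads as follows.

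- **Objective (1.3).** The aim is to learn whether adding IPACK "is superior to an isolated adductor canal block in decreasing postoperative pain, decreasing opioid consumption". This is superiority. No equivalence margin or smallest relevant difference appears anywhere.
- **Analysis (6.2).** "Normally distributed data such as the primary outcome variable will be compared using the two-sample t-test". The fallback is: "In the case that the data are not normally distributed, the Wilcoxon rank-sum test will be used instead". Sections 6.1 and 6.2 plan no confidence interval for the difference between arms.
- **Sample size (6.3).** "Using a 2-sided, 2-sample t test, an α value of 0.05", the plan concludes that "42 subjects were needed per group to detect a moderate effect size with a power of 0.80". It enrols 50 per arm to cover dropout and raise power. The effect size has no number.
- **Potential benefits (5.2).** The possible benefit to future patients is introduced with "If the study is not inconclusive", so the document elsewhere accepts that the trial may settle nothing.

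**The concern.** A non-significant superiority test has two possible explanations: the effect is too small to matter, or the trial was not precise enough to show it. Telling them apart requires a difference that counts as relevant and an interval to compare with it. The plan has neither, and section 1.2 assigns every non-significant result to the first explanation. The inconclusive outcome that section 5.2 allows for has no place in that rule.

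What is at stake is the published conclusion. A null result is a realistic prospect: section 1 reports that earlier IPACK studies in arthroplasty found no significant difference in narcotic use. A reader would take a statement of no relevant difference as evidence against the block, when the data might still be compatible with the full effect the trial was built to detect.

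**Working it through.** **Inputs.** From 6.3: two-sided two-sample t test, alpha 0.05, power 0.80, 42 per group needed, 50 per arm enrolled. From section 2.1: equal allocation. Not given: the effect size, its SD and the expected dropout rate.

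**1. The plan's own figure.** The word used for the effect size in 6.3 has no numerical value, so 42 cannot be reproduced from it directly. Solving backwards with the normal approximation:

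d = (z₀.₉₇₅ + z₀.₈₀) × √(2/n) = (1.960 + 0.842) × √(2/42) = 0.611

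The exact noncentral t calculation returns 42 per group for d between 0.619 and 0.626. I use d = 0.62.

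**2. Chance of a non-significant result.** At the effect used for sizing, with 42 per arm, this is 1 − 0.80 = 20%, whatever effect was meant. The other figures use the noncentral t distribution with 2n − 2 degrees of freedom and noncentrality d√(n/2), which at d = 0.62 is 2.84 for n = 42 and 3.10 for n = 50.

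| True difference (SD) | 42 per arm | 50 per arm |
|---|---|---|
| 0.62 | 19.8% | 13.4% |
| 0.50 | 38.0% | 30.3% |
| 0.40 | 55.9% | 49.2% |
| 0.30 | 72.6% | 68.2% |

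Over the whole range of d that gives 42 per group, the figure for 50 per arm is 12.7% to 13.5%. It assumes no loss. At the lower end of that range of d (0.619) it is about 15% with 48 analysable per arm and 17% with 45.

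**3. What a non-significant result leaves open.** The half-width of the 95% confidence interval, in SD units, is t(0.975, 2n − 2) × √(2/n): 0.434 for n = 42 and 0.397 for n = 50. A result that just misses significance therefore has an interval from 0 to 2 × 0.434 = 0.87 SD (42), or 2 × 0.397 = 0.79 SD (50). With 50 per arm, any observed reduction from 0.62 − 0.397 = 0.22 SD up to 0.40 SD is non-significant while its interval still contains 0.62 SD. With 42 the band is 0.19 to 0.43 SD.

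**4. Two reading rules compared.** The rules are section 1.2 as written, and a rule that claims no relevant reduction only when the result is non-significant and the interval excludes 0.62 SD. Figures are from 400,000 simulated trials per cell with estimated SD (42 / 50 per arm).

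| True difference | Section 1.2 says no relevant difference | Interval rule says so | Interval rule says inconclusive |
|---|---|---|---|
| 0.62 SD (claim wrong) | 19.9% / 13.3% | 2.5% / 2.5% | 17.4% / 10.7% |
| 0 (claim right) | 95% / 95% | 77.8% / 84.2% | 17.2% / 10.9% |

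**5. If the rank test is used.** For a 0.62 SD shift (6,000 simulated trials per cell), misses are 22% / 15% with normal data and 9% / 5% with gamma data of shape 2, an assumed degree of skew.

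**The case against.** - **These passages do not strictly contradict each other.** Section 6.3 accepts a type II error and section 1.2 says how non-rejection will be described; both can stand on the page. Section 5.2 is an aside that does not address the analysis. This is fair: the fault is one of inference, reading absence of evidence as evidence of absence. That makes the sentence no sounder.
- **The sentence drives no computation.** It stands in section 1, and no test, population or stopping decision depends on it, so a careful author could avoid the misreading when reporting. This limits the weight of the point. But it is the only interpretation laid down in advance, and a margin chosen after seeing results by arm would carry little conviction.
- **A miss is a wrong claim only if the design effect is clinically relevant, which the plan never says.** Correct. I infer relevance from the plan having been sized to detect that effect. If smaller effects also matter, the problem grows.
- **The percentages are generic.** Any trial with 80% power misses 20% of the time, and the 2.5% follows by construction when the margin equals the true effect. Also true: the defect is the instruction to report those misses as evidence of no relevant effect. With skewed data and the rank test the miss rate falls to 9% or 5%, still above 2.5%.
- **The repair has costs.** A margin smaller than 0.62 SD makes the claim hard to earn. This stands and is quantified under the fix.

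**Conclusion.** The point holds. Followed as written, section 1.2 leads to a conclusion that the design cannot support. If the effect the plan is sized for is real, the sentence produces a false statement of no relevant difference in 20% of trials with 42 analysable per arm and about 13% with 50, against 2.5% under a confidence-interval rule.

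The 20% needs only the power stated in 6.3. The 13% also assumes d = 0.62, the planned t test and no loss of patients. Calling either figure an error assumes that the design effect is clinically relevant. The primary test remains valid; what should be corrected is the stated meaning of a null result.

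**What to change.** 1. **Section 1.2.** Replace the last sentence with: *A non-significant result will be read as no clinically relevant reduction only if the upper limit of the 95% confidence interval for the reduction with IPACK lies below [smallest relevant reduction, mg oral morphine equivalent, fixed with its justification before any comparison by arm]. Otherwise it will be reported as inconclusive.*
2. **Section 6.2.** Add: *The primary result will be reported as the between-arm difference with its 95% confidence interval (mean difference with the t test; Hodges-Lehmann shift with the rank test).*
3. **Section 6.3.** State the effect size behind the 42 per group, so that it can be compared with the margin.

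Before a margin in mg can be set, the primary window must be reconciled: the Protocol Summary and 1.3 give 72 hours, while 1.2, 6.1 and 6.2 give 24 hours.

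**Cost.** No extra patients or data: three short text edits and one decision on the margin. The price is that some true nulls will be reported as inconclusive. With no true difference and a margin of 0.62 SD this is about 11% of trials with 50 per arm and 17% with 42. With 50 per arm it rises to 28% at a margin of 0.50 SD and 47% at 0.40 SD. If the investigators cannot agree on a margin, the minimum repair is to say that non-rejection would mean superiority was not shown, and still report the interval. That removes the false claim but gives up the possibility of concluding that there is no relevant reduction.
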